- c On day 15 of cycle 1 and at the beginning of each subsequent treatment cycle, study drug compliance should be reviewed with the patient and a sufficient supply of drug should be dispensed to the patient to take at home. A final drug compliance assessment should be done at the End of Treatment visit (if applicable) and any remaining drug should be retrieved from the patient.
- d May be done up to 72 hours prior to day 1 of each treatment cycle.
- e Serum or urine pregnancy test required on day 1 of each treatment cycle in women of child-bearing potential only.
- f CT scan s of the chest/abdomen/pelvis required at baseline. Scans will be repeated every 2 cycles. Only abnormal scans need to be repeated after baseline.
- g Head CT or MRI scan required at baseline for patients with a history of treated brain metastases only.
- h There is a +/- 7 day window on day 1 of all subsequent cycles to accommodate scheduling issues.
- i Patients must be followed for AEs for 30 calendar days after the last dose of study drug. Patients who have not progressed at the time of study discontinuation will be followed for disease assessment only every 3 months ( $\pm 1$  month) until disease progression.
- j. On CD15, vital signs only. No physical exam is required on this visit.

STUDY DRUG(S): REGORAFENIB/AFATINIB/CABOZANTINIB FINAL PROTOCOL DATE: 6 MAY 2016 Amendment Number 2:23 January 2018 CONFIDENTIAL SARAH CANNON DEVELOPMENT INNOVATIONS STUDY NUMBER: PRO 10 VERSION 3

Sarah Cannon Development Innovations Contact Information:	Sarah Cannon Development Innovations [name] [name] [contact]
Study Chair:	[name] Sarah Cannon Development Innovations [name] [name] [contact]
Safety Dept. [contact]
Safety Dept. Email:	[contact]
Regulatory Phone # Regulatory Email:	[name] [contact]

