#### CONFIDENTIAL

STUDY DRUG(S): REGORAFENIB/AFATINIB/CABOZANTINIB INNOVATIONS STUDY NUMBER: PRO 10 FINAL PROTOCOL DATE: 6 MAY 2016 AMENDMENT NUMBER 2:23 JANUARY 2018 SARAH CANNON DEVELOPMENT

Patients who discontinue study treatment prior to the occurrence of disease progression will be followed for disease assessment only every 3 months ( $\pm 1$  month) from the date of last dose of study drug until disease progression.

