## 10.2.2 Efficacy Analysis

All efficacy analyses will be performed using the Intent-To-Treat Population.

- Overall Response Rate (ORR) is defined as the proportion of patients with confirmed complete response (CR) or partial response (PR (i.e. 2 CRs or PRs at least 4 weeks apart) according to the RECIST v1.1.
- Clinical Benefit Rate (CBR) is defined as the proportion of patients with CR, PR or SD ≥ 6 months according to the RECIST v1.1.
  - For ORR and CBR, patients without a post-baseline tumor assessment will be classed as not evaluable (NE) and considered as non-responder.
- Time to treatment failure (TTF) is measured from the first day of treatment until the patient is removed from study for toxicity, disease progression, patient choice, or death.
- Progression Free Survival (PFS) is defined as the time from the first day of study drug administration (Day 1) to disease progression as defined by the RECIST v1.1, or death on study. Patients who are alive and free from disease progression will be censored at the date of last tumor assessment.

For ORR and CBR, the estimates and the associated 95% CI (based on the Clopper-Pearson method) in each treatment group will be calculated.

For PFS, Kaplan-Meier curves will be generated and the median time to event and the associated 95% CI will be provided.

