#### **Reporting Period for Adverse Events**

All AEs regardless of seriousness or relationship to the FDA-approved targeted agents (called study treatment), spanning from the start of study treatment, until 30 calendar days after discontinuation or completion of study treatment as defined by the clinical study for that patient, are to be recorded on the corresponding screen(s) included in the eCRF.

All AEs resulting in discontinuation from the study should be followed until resolution or stabilization. All new AEs occurring during this period must be reported and followed until resolution unless, in the opinion of the investigator, the AE or laboratory abnormality/ies are not likely to improve because of the underlying disease. In this case, the investigators must record his or her reasoning for this decision in the patient's medical record and as a comment on the eCRF screen.

After 30 days of completion of protocol-specific treatment or discontinuation, only AEs, SAEs, or deaths assessed by the investigator as treatment related are to be reported.

CONFIDENTIA	L
STUDY DRUG(S): REGORAFENIB/AFATINIB/CABOZANTINIB	SARAH CANNON DEVELOPMENT
INNOVATIONS STUDY NUMBER: PRO 10	
FINAL PROTOCOL DATE: 6 MAY 2016	VERSION 3
Amendment Number 2:23 January 2018	

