# 11.3.4 Deaths

Deaths that occur during the protocol-specified AE reporting period that are attributed by the Investigator solely to progression of disease will be recorded on the "Study Discontinuation" eCRF screen. All other on study deaths, regardless of attribution, will be recorded on an SAE Report Form and expeditiously reported to the Sarah Cannon Development Innovations Safety Department.

When recording a SAE with an outcome of death, the event or condition that caused or contributed to the fatal outcome should be recorded as the single medical concept on the SAE Report Form and Adverse Event screen of the eCRF. If the cause of death is unknown and cannot be ascertained at the time of reporting, record "Death NOS" on the eCRF Adverse Event screen. During post-study survival follow-up, deaths attributed to progression of disease will be recorded only on the "After Progressive Disease Follow-Up" eCRF screen.

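### PFS has no event or censoring rule, and no secured data, for a patient who stops drug without progression and dies more than 30 days later

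*Combined protocol and SAP*

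**What the plan says.** Section 10.2.2 defines PFS as the time from the first day of study drug "to disease progression as defined by the RECIST v1.1, or death on study". Its censoring rule reads: "Patients who are alive and free from disease progression will be censored at the date of last tumor assessment". The document does not define when a patient is on study.

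Follow-up and death recording are set out in four other places:

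- Section 7.4: patients who stop treatment before progression "will be followed for disease assessment only every 3 months", with a one-month window, until progression.
- Schedule of assessments, footnote i: "Patients who have not progressed at the time of study discontinuation will be followed for disease assessment only every 3 months".
- Section 11.1.5, reporting period: once 30 days have passed since treatment ended, "only AEs, SAEs, or deaths assessed by the investigator as treatment related are to be reported".
- Section 11.3.4: within the adverse-event reporting period, deaths due solely to progression go on the study discontinuation screen. For the rest, "All other on study deaths, regardless of attribution, will be recorded on an SAE Report Form". It then adds: "During post-study survival follow-up, deaths attributed to progression of disease will be recorded only on the" eCRF screen for follow-up after progressive disease.

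No schedule sets up a survival follow-up, and neither Section 7.4 nor the footnote names vital status or date of death.

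**The concern.** The event rule and the censoring rule should between them cover every patient, and here they do not. Someone who stops for toxicity or by choice without progression, lives past the 30-day window and dies before the next scan shows progression is not plainly an on-study death. Being dead, that patient also fails the condition for censoring. The analyst must then improvise, and the likely choices (censor at the last scan, or leave the patient out) both remove a failure from the curve.

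The collection rules add to the problem. If the date of death is not asked for prospectively, it may not be available when the analysis is run. PFS is a stated secondary objective, reported by arm with Kaplan-Meier curves and no control group, so there is no comparator in which such a bias could cancel.

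**Working it through.** **1. The plan's own figure.** The only sizing figure is for response rate (Sample Size Considerations): 40 evaluable patients per arm, at least 8 responders, 10% against 25%. The exact binomial gives P(X ≥ 8 | 40, 0.10) = 0.0419 and P(X ≥ 8 | 40, 0.25) = 0.818. No smaller n meets both one-sided 5% and 80% power, so the figure reproduces. PFS does not enter it, and the plan states no PFS figure to reproduce.

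**2. Which deaths have a rule.** Take a patient who stops drug without progression.

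| What happens next | Recorded? | PFS rule? |
|---|---|---|
| Death within 30 days of the last dose | Yes (11.3.4) | Event |
| Progression on a 3-monthly scan | Yes (7.4) | Event |
| Alive without progression | Yes (7.4) | Censored at last assessment |
| Death after 30 days, before a progression scan | Only if treatment-related (11.1.5) or, possibly, attributed to progression (11.3.4) | None on the natural reading |

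Only the last row is affected.

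**3. Size if such deaths are censored.** The documents give the scan interval on drug (8 weeks: c = 56/30.4375 = 1.84 months), the interval afterwards (3 months) and the 30-day limit. Everything else is assumed:

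- time to progression is exponential with median m = 3 or 5 months, rate λ = ln 2 / m;
- stopping before progression is exponential with rate λ·s/(1 − s), so that a share s = 10% to 40% stop first;
- survival after stopping is exponential with median 4 or 8 months, independent of progression;
- every death in the last row is unrelated to treatment and unrecorded.

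Progression is dated at the next scheduled scan. Each scenario simulates 400,000 patients and compares Kaplan-Meier PFS with every death counted against PFS with the last-row deaths censored at the last tumor assessment.

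| m (months) | s | Median survival after stop (months) | Lost deaths per 40 | 6-month PFS, counted → censored | Rise (points) |
|---|---|---|---|---|---|
| 3 | 10% | 4 | 1.7 | 0.270 → 0.276 | 0.6 |
| 3 | 10% | 8 | 1.2 | 0.278 → 0.282 | 0.4 |
| 3 | 40% | 4 | 6.7 | 0.234 → 0.264 | 3.0 |
| 3 | 40% | 8 | 4.7 | 0.277 → 0.297 | 2.0 |
| 5 | 10% | 4 | 2.0 | 0.453 → 0.460 | 0.7 |
| 5 | 10% | 8 | 1.5 | 0.461 → 0.465 | 0.4 |
| 5 | 40% | 4 | 8.2 | 0.404 → 0.442 | 3.8 |
| 5 | 40% | 8 | 6.1 | 0.442 → 0.467 | 2.5 |

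Results for s = 20% and 30% lie between these rows. The direction is upward in all 16 scenarios. The median stays at 3.68 months (2 × 1.84) or 5.52 months (3 × 1.84), because it falls on a scheduled scan date. The model uses exact scan dates and very large samples. It does not cover leaving patients out altogether, or deaths linked to unobserved progression.

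**The case against.** The case against is substantial, and much of it narrows the point.

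- **Early deaths are safe.** Section 11.3.4 records every death in the reporting period, so a death soon after stopping drug is not lost. This stands.
- **Section 11.1.5 is a safety rule.** It does not say that efficacy dates go uncollected. True, but no other section asks for those dates either.
- **The on-study limit is undefined.** Section 7.4 speaks of stopping study treatment and keeps these patients in protocol follow-up, so their deaths could be read as on study. The weight of usage is the other way. Footnote i places them after study discontinuation, the definition of time to treatment failure removes them from study, and Section 11.3.4 separates on-study deaths from a post-study period. The ambiguity is itself a defect in an event definition.
- **Section 11.3.4 mentions survival follow-up.** It covers only progression-attributed deaths, on a screen titled for patients past progression, whose PFS event is already fixed. Section 13.3.1.1 seeks vital status only from patients who revoke authorization.
- **PFS is secondary and descriptive.** This stands, and it limits the consequence.

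Three stronger readings are tempting. A reader might infer that PFS is certainly overstated. The documents do not show this, because the number of such deaths and the analyst's handling are both unknown. A reader might also expect the median to inflate by 1/(1 − f), or about 3%, 5% or 11% if f = 3%, 5% or 10% of events are censored. Those shares have no source in the documents, and the formula ignores the scan schedule, under which the median did not move. Finally, because the baseline CT may precede Day 1 by up to 28 days (Section 7.1), a living patient with no later scan would get a negative PFS time. That patient leaves the risk set before any event, so censoring at Day 1 gives the same estimate.

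**Conclusion.** The gap is real but narrow. On the natural reading, a death more than 30 days after stopping drug and without documented progression has neither an event rule nor a censoring rule, and the plan does not secure its date. PFS can be biased upward as a result. Under the assumed rates, about 1 to 8 patients in an arm of 40 would be affected and 6-month PFS would rise by 0.4 to 3.8 percentage points, with no shift in the median. Those figures rest on assumed rates of stopping and death and on independence of death and progression, because the documents supply no rates. The response-rate decision rule is untouched. This should be corrected because the date of death may not be recoverable later, but it does not threaten the primary conclusion.

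**What to change.** - In Section 10.2.2, define the PFS event as the first of RECIST 1.1 progression or death from any cause, on or off study drug. This removes the dependence on an undefined on-study status. State also how a death after missed assessments is handled.
- In Section 7.4 and footnote i, add vital status and date of death, regardless of cause, to the existing 3-monthly contact.
- Reconcile Sections 11.1.5 and 11.3.4 so that the safety reporting limit does not restrict death data needed for efficacy. Either schedule the survival follow-up that Section 11.3.4 mentions or remove the reference.
- As a tidy convention only, censor living patients with no post-baseline scan at Day 1.

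The cost is a few sentences and one extra eCRF field, with no added visits or scans. Reported PFS may be slightly lower.

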## 10.2.3 Safety Analysis

Safety will be assessed through the analysis of the reported incidence of treatment-emergent AEs. Treatment-emergent AEs are those with an onset on or after the initiation of therapy, and will be graded according to NCI CTCAE v. 4.03. A copy of CTCAE scoring system may be downloaded from: http://evs.nci.nih.gov/ftp1/CTCAE/CTCAE\_4.03\_2010-06-14\_QuickReference\_8.5x11.pdf.

The AEs will be coded using Medical Dictionary for Regulatory Activities (MedDRA), and summarized using system organ class and preferred term by treatment arm for all patients in the

CONFIDENTIAL	
STUDY DRUG(S): REGORAFENIB/AFATINIB/CABOZANTINIB	SARAH CANNON DEVELOPMENT
INNOVATIONS STUDY NUMBER: PRO 10	
FINAL PROTOCOL DATE: 6 MAY 2016	VERSION 3
Amendment Number 2:23 January 2018	

Safety Population. In addition, summaries of SAEs, AEs leading to treatment discontinuation, AEs by maximum NCI CTCAE grade, and AEs related to study treatment will also be presented by treatment arm.

Other safety endpoints including laboratory results, vital signs and ECG findings will be summarized for all patients in the Safety Population

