## 5. STUDY DESIGN

This four-arm pilot phase II study will evaluate the preliminary antitumor activity of selected commercially available molecularly matched targeted therapies in patients who have failed first line treatment for one of the following tumor types: (1) non-small cell lung cancer, (2) urothelial carcinoma, (3) non-colon gastrointestinal cancers, and (4) upper aerodigestive tract cancers. Patients will be profiled with next-generation sequencing technology results known prior to consideration for enrollment on this protocol. Patients with the specified tumor types demonstrating one of the genomic alterations described in Table 1 may be assessed for protocol eligibility and treatment. Patients with a genomic alteration that is not described in Table 1 but is covered by a targeted agent in Table 2 will also be eligible. All eligible patients will receive one of the FDA-approved targeted agents at the recommended dose outlined in Table 2. Dose modifications will be implemented based on criteria outlined in the product package insert for each individual agent. Patients will be re-evaluated for treatment response after receiving 8

CONFIDENTIAL

STUDY DRUG(S): REGORAFENIB/AFATINIB/CABOZANTINIB INNOVATIONS STUDY NUMBER: PRO 10 FINAL PROTOCOL DATE: 6 MAY 2016 AMENDMENT NUMBER 2:23 JANUARY 2018 SARAH CANNON DEVELOPMENT

weeks of oral therapy (with the exception of regorafenib which is dosed intermittently for 21 out of every 28 days). Response to therapy will be assigned using RECIST v1.1 (see Appendix E). Patients who have objective response (OR) or stable disease (SD) will continue treatment with re-evaluations every 8 weeks, until the time of tumor progression or intolerable treatment-related side effects. If a patient was not profiled with Foundation One® prior to study enrolment, Sarah Cannon Development Innovations shall use reasonable efforts to collect and send to Foundation Medicine adequate tumor tissue meeting the tissue specimen requirements for Foundation One® for retrospective profiling that will be completed and compared to the profiling report provided at study entry.

A total of 160 patients are planned to be enrolled on the trial (40 patients per study arm).

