#### 5.1 Treatment Plan

#### 5.1.1 FDA-Approved Targeted Agents

The FDA-approved targeted agents that will be administered during the study are outlined in Table 2. Study drugs will be provided by the manufacturer and will not be billed to the patient's insurance as the proposed usage is considered off-label for the agent. The treating physician will decide which targeted agent will be prescribed based on the genomic alterations per tumor type and the targets listed in the package insert for each agent that are outlined in Tables 1 and 2. Patients with a genomic alteration that is not described in Table 1 but is covered by a targeted agent in Table 2 will also be eligible. The Medical Monitor will verify the genomic alteration and prescribed targeted agent when the patient is registered for the trial.

All patients entering this study will receive one of the targeted agents orally either daily continuously at the prescribed dose listed in Table 2 (except for regorafenib which is dosed daily for 21 out of every 28 days). Patients will be instructed to take the medication with or without food as directed in the product package insert. The time of day for administration of study drug should be consistent.

If the patient misses a dose of study drug, the patient should skip the missed dose and take the next dose as scheduled.

If vomiting occurs after taking the study medication, the patient should be instructed not to retake the dose. Patients should take the next scheduled dose of study drug. If vomiting persists the patient should contact the investigator.

No routine prophylactic antiemetics will be given. However, antiemetics may be administered for the treatment of nausea and vomiting when they occur, and may be given prophylactically afterwards.

Study drug compliance will be assessed by pill counts on Day 1 of each cycle. The research staff will count and document the amount of study drug taken and returned by the patient.

CONFIDENTIAL

STUDY DRUG(S): REGORAFENIB/AFATINIB/CABOZANTINIB INNOVATIONS STUDY NUMBER: PRO 10 FINAL PROTOCOL DATE: 6 MAY 2016 AMENDMENT NUMBER 2:23 JANUARY 2018 SARAH CANNON DEVELOPMENT

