#### **Sample Size Considerations**

The design of this trial uses an exact single-stage design for each of the four arms. (A'Hern 2001) For this investigation, it has been determined that an ORR (CR + PR) of 10% or worse has low activity in line with standard of care. An ORR of 25% (or better) is considered to indicate interesting activity. Using a one-sided alpha of 5% and power of 80%, 40 evaluable patients will be required in each arm. A minimum of 8 responders in a particular arm would indicate that the corresponding tumor type would be worthy of further investigations.

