#### **10.3** Analysis Time Points

#### **10.3.1** Final Analysis

The final analysis of the study will occur when the required number of response evaluable patients has been reached in each treatment arm.

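### Adverse events are tabulated by tumour-type arm, so no planned table gives an adverse-event rate for any of the three drugs

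*Combined protocol and SAP*

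**What the plan says.** Section 10.2.3 (Safety Analysis) has adverse events coded and "summarized using system organ class and preferred term by treatment arm". It then lists summaries of serious events, events leading to discontinuation, events by maximum grade and related events, ending "AEs related to study treatment will also be presented by treatment arm". The following sentence reads "Other safety endpoints including laboratory results, vital signs and ECG findings will be summarized for all patients in the Safety Population"; it names an analysis set and no grouping variable.

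The arms are described elsewhere:

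- **Sample Size Considerations:** there are four arms, "40 evaluable patients will be required in each arm", and the success rule is "A minimum of 8 responders in a particular arm would indicate that the corresponding tumor type would be worthy of further investigations".
- **Section 10.3.1:** the final analysis takes place "when the required number of response evaluable patients has been reached in each treatment arm".
- **Section 5:** enrolment is planned at 160, 40 per arm.
- **Section 1.2, Table 2:** there are three drugs.
- **Section 5.1.1:** "The treating physician will decide which targeted agent will be prescribed based on the genomic alterations per tumor type". No number of patients is fixed for any drug.

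No section plans a safety table by drug received.

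**The concern.** If an arm is a tumour type and its patients take up to three different drugs, a by-arm adverse-event rate is an average over drugs. It describes toxicity in, say, the urothelial patients of this trial under whatever mix of drugs they received. It does not give the rate on any one drug, even when the mix is known.

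The protocol itself treats some risks as specific to a drug. Exclusions 14 and 15 in Section 3.2 add haemorrhage and perforation or fistula restrictions for cabozantinib only, on top of the general bleeding exclusion 13. Dose modification in Section 6 follows each agent's own package insert. Section 5.1.1 regards the use as off-label, so toxicity by drug in these populations is information a reader will want, and the planned tables do not supply it.

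**Working it through.** **1. What a treatment arm is.** The term is not formally defined, so the passages have to be set side by side.

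- There are four arms and three drugs, so arms cannot be drugs one for one.
- The eight-responder rule in Sample Size Considerations is applied to an arm and leads to a conclusion about a tumour type.
- Section 10.3.1 uses the same term as Section 10.2.3 for the unit that must reach its required number. Sample Size Considerations sets that number at 40 for each of the four arms.

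The tumour-type reading is the one that fits all of these.

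**2. The plan's own figure.** With X binomial (n = 40) and success at X ≥ 8:

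- P(X ≥ 8 | ORR 10%) = 0.0419, within the one-sided 5%.
- P(X ≥ 8 | ORR 25%) = 0.818, above 80%.
- n = 40 is the smallest sample size that meets both limits, and 4 × 40 = 160.

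The stated design reproduces, and nothing below changes it.

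**3. What a by-arm rate can show.** Let s be one drug's share of an arm, p the event rate on that drug and q the rate on the others:

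arm rate = p·s + q·(1 − s)

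This is one equation in two unknowns, so knowing s does not give p. At s = 0.50 an arm rate of 15% arises from:

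- p = 30%, q = 0%: 0.5 × 0.30 + 0.5 × 0 = 0.15
- p = 15%, q = 15%: 0.5 × 0.15 + 0.5 × 0.15 = 0.15
- p = 0%, q = 30%: 0.5 × 0 + 0.5 × 0.30 = 0.15

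**4. Illustration.** The shares and rates are assumed, because the documents give neither. Take p = 30% in a 40-patient arm. The intervals are 95% Clopper-Pearson, with limits Beta(0.025; x, n − x + 1) and Beta(0.975; x + 1, n − x).

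| Share s | Arm rate, q = 0% | Count and 95% CI | Arm rate, q = 15% |
|---|---|---|---|
| 25% | 7.5% | 3/40 (1.6–20.4%) | 18.75% |
| 50% | 15% | 6/40 (5.7–29.8%) | 22.5% |
| 75% | 22.5% | 9/40 (10.8–38.5%) | 26.25% |

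The dilution is smaller when the other drugs also cause the event.

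**5. By arm against by drug on the same events.** Take s = 25% in all four arms, p = 30% and q = 15%.

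- Each arm: 0.25 × 0.30 + 0.75 × 0.15 = 18.75% expected, identical in all four.
- On the drug: 4 × 10 = 40 patients and 0.30 × 40 = 12 events, so 12/40 = 30% (16.6–46.5%).
- On the others: 4 × 30 = 120 patients and 0.15 × 120 = 18 events, so 18/120 = 15% (9.1–22.7%).
- Check: (12 + 18)/160 = 18.75%.

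The by-arm and by-drug intervals estimate different quantities, so neither is expected to cover the other. The drug mix may differ between arms, but alterations outside Table 1 are eligible if a listed drug covers them, so the documents do not establish that it will.

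**The case against.** **The term is undefined.** Section 10 speaks of study arm (10.2.1), treatment group (10.2.2) and treatment arm (10.2.3, 10.3.1). In a safety section a reader could take the last to mean drug, and then the by-drug table is already planned. The wording is loose, and that part stands. The drug reading conflicts with the count of four arms and with the use of the same term in Section 10.3.1. If drug was meant, Section 10.2.3 still needs a sentence saying so.

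**Drug-level safety is handled elsewhere.** Investigators judge relatedness to the study drug, Section 11.4 sends serious events to the relevant manufacturer, and Section 11.4.2 routes IND safety reports by drug. This covers individual cases. It gives no incidence with a denominator.

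**The illustration is built from assumptions.** That is correct. It shows how the grouping behaves and says nothing about what this trial will find.

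**By-drug groups may be small.** There is no quota per drug, and cabozantinib was added only by Amendment 2. This stands and limits what the tables can support.

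**Nothing hangs on the tables.** Section 2 lists only efficacy objectives, no decision rule uses safety rates, and the tables could be produced later from the same data. This settles the weight of the point. Prespecifying the tables still ensures that they are produced and fixes the grouping before results are seen.

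**Laboratory and vital-sign results might be meant as one pooled summary.** That is possible. However, the adverse-event sentence names the same analysis set and a grouping as well, so naming the set does not settle the grouping. This is a minor matter of missing detail.

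**Conclusion.** The point holds. Under the tumour-type reading, which is the only one that fits the number of arms, the success rule and Section 10.3.1, the planned tables give adverse-event rates averaged over up to three physician-chosen drugs and no rate for any drug. How much this hides depends on shares and rates that the documents do not give. In the worked example a 30% against 15% difference becomes the same expected 18.75% in every arm. Sample size, error rates, power and the primary response analysis are unaffected. It is a worthwhile improvement in safety reporting, not a flaw in the design.

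**What to change.** In Section 10.2.3:

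- Add summaries by drug received, pooled over tumour types, of all adverse events, serious events, events leading to discontinuation, maximum-grade events, related events, laboratory results and vital signs.
- Keep the tumour-type tables, and make plain that treatment arm there means tumour type.
- State the grouping used for laboratory and vital-sign results.
- Label the by-drug tables descriptive, because drug is confounded with genomic alteration and tumour type and the groups may be small and unequal.

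A by-drug table of on-treatment ECG findings is not requested, since the only ECG scheduled is the baseline one in footnote a to the synopsis schedule of assessments.

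The cost is one or two sentences and a few tables. No new data are needed: the Medical Monitor verifies the prescribed drug at registration (Section 5.1.1), and adverse events, laboratory tests and vital signs are already collected on treatment (Section 7.3). The drawback is more output, some of it with small cells that must not be read as comparisons between drugs. The primary response analysis by tumour type stays as it is.
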